
 Previous drug treatment in the pre-index period, based on appropriate ATC group level 
 Percentage of patients who received specific treatments (most common 10 treatments as observable for above samples) with at least two prescriptions in the pre-index period. 
Documentation referring to the 12 months follow-up after index date (for patient subgroups: 24 months/36 months follow-up, or complete follow-up period)
 
 For patients with available data resulting from a disease management program (DMP) 
 Weight [kg] (reported MIN, MAX and MEAN during follow-up period) Height [cm] Blood pressure (reported MIN, MAX and MEAN during follow-up period) Non-drug treatment recommendations Exacerbations (number and severity) FEV₁ (reported MIN, MAX and MEAN during follow-up period) Smoking status if applicable Drug treatment with long-acting bronchodilators (incl. separate reporting for respective agent classes beta-agonists, anticholinergics, methylxanthines) Drug treatment with short-acting agents Drug treatment with anti-inflammatory drugs (ICS, PDE-4, macrolides) Top-10 prescribed non-COPD drug therapies (based on ATC codes on appropriate level) 			

Name of company: Boehringer Ingelheim			
Name of finished medicinal product: COPD medication of any type			
Name of active ingredient: COPD medication of any type, ATC code R03			
Protocol date: 16 Oct 2019	Study number: 1237-0092	Version/Revision: 1.0	Version/Revision date: Not applicable

 • Antibiotics for systemic use (based on ATC J02AA) • Antibiotics in combination with corticosteroids (based on ATC D07C) • Systemic/oral corticosteroids (SCS/OCS; based on ATC R01AD02; D07AA01; D10AA02; H02AB04) • All-cause hospitalizations 
 ○ Among them: hospitalizations with COPD as main diagnosis (ICD-10 J44.-) • Among them: hospitalizations with a COPD exacerbation as main diagnosis (ICD-10 J44.1) • Exacerbations as documented by outpatient pneumologists (ICD-10 J44.1) • GP visits and pneumologists' visits and visits to other specialists • Prescription of COPD-associated aids 
 ○ Oxygen therapy • Date of death, if patient died during follow-up period (for censoring and time to event analyses). 			

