 - According to both guidelines mentioned above, a triple combination treatment LABA+LAMA+ICS should only be prescribed if a patient experienced at least two exacerbations or one severe exacerbation requiring an inpatient treatment in the history of the disease. Based on this, the following percentage will be reported:
 - Percentage of patients not treated in line with the 2012/2018 guideline
 - Only 1 or less confirmed outpatient diagnoses and no inpatient diagnosis of a COPD exacerbation (ICD-10 J44.1) before date of prescription of a triple therapy.
- COPD-12, for the whole follow-up period (12 months)
 - A treatment intensification (mono to dual therapy, mono to triple or dual to triple therapy) should generally be accompanied by a thorough application of recommended diagnostic measures, according to the 2012/2018 guidelines. For these, typically, general practitioners (GPs) do not have the necessary infrastructure. Based on this, the following percentage will be reported:
 - Percentage of patients who received a treatment intensification without any previous visit of a pneumologist or hospital (same quarter or previous quarter)

Sensitivity analysis

In a first sensitivity analysis, those of above patients will be included for whom at least one ICD-10 COPD code that provides information up to the 5th level is documented: These subcodes include information about FEV₁ level. For patients for whom such a subcode is available, in this analysis, disease severity will be defined based on this information, which is mainly important when applying the 2012 guideline.

¹⁶ Of those patients starting with triple therapy of LABA+LAMA+ICS at time of incident COPD diagnosis, physician visits (separately of cardiologists, pneumologists) and measures of lung function (DMP-dataset only) before or at index date will be reported. Time since last physician visits to a cardiologist or a pneumologist will be reported too.

In a second sensitivity analysis, the sample COPD DMP-12 will be analyzed. In the DMP data set, additional documentation about exacerbation history and FEV₁ is available. Based on these data, the following analyses are planned:

- COPD DMP-12, at index date: no additional analysis, as DMP data will not be available for the pre-index period
- COPD DMP-12, at first date of an observed LABA+LAMA+ICS combination, which is not the index date; patients for whom at least one DMP entry before date of prescription of above combination will be included

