 - According to both above guidelines, a triple combination treatment LABA+LAMA+ICS should only be prescribed if a patient experienced at least 2 exacerbations or one severe exacerbation requiring an inpatient treatment in the history of the disease. In addition, the 2012 guideline also recommended such a treatment in case a FEV₁<50% could be observed. Based on this, the following percentages will be reported:
 - Percentage of patients not treated in line with the 2018 guideline
 - Only one or no confirmed outpatient diagnosis and no inpatient diagnosis of a COPD exacerbation (ICD-10 J44.1) before date of prescription of a triple therapy.
 - Percentage of patients not treated in line with the 2012 guideline
 - Only one or no confirmed outpatient diagnosis and no inpatient diagnosis of a COPD exacerbation (ICD-10 J44.1) and only one or no outpatient diagnosis and no inpatient exacerbation diagnoses as documented in the DMP dataset and no documented FEV₁ value <50%.

Second Secondary

Description of exacerbation frequency

For all samples (COPD-12, COPD-24, COPD 36, COPD DMP-12, COPD DMP-24, COPD DMP-36, COPD-FULL DATA), exacerbation frequency in the pre-defined follow-up periods (12 months, 24 months, 36 months, patient-individual follow-up times) will be described. Because of the higher diagnosis validity, in the main analysis only severe exacerbations leading to an inpatient hospitalization (COPD exacerbation documented as main diagnosis: ICD-10 J44.1) will be considered. Moreover, in a separate analysis proxies will be used to estimate non-severe exacerbations. Therefore prescriptions of SCS/OCS either separately or in combination with antibiotics, will be considered as proxy for the treatment of a non-severe exacerbation (without an inpatient hospitalization). Exacerbation frequency (once for severe and once for non-severe exacerbations) will be reported as percentage of patients having experienced at least 1 exacerbation, exactly 1 exacerbation, exactly 2 exacerbations, exactly 3 exacerbations, and >3 exacerbations, and as mean number of exacerbations per observed patient-year.

Third Secondary

Description of health care resource use and direct treatment cost

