Health care resource use (HCRU) and direct cost will be reported as described in Table 3, based on the perspective of a German sickness fund and based on prices of the respective years as reported in the claims data base. HCRU and cost will be reported for the following samples in separate analyses: COPD-12, COPD-24, and COPD-36.

Generally, HCRU/cost will be reported per observed patient year. HCRU and cost will be compared between the following patient groups:

- Patients participating in a DMP versus those who did not participate
- Patients having received early (first 3 months after index date) a triple combination therapy (LABA+LAMA+ICS) versus those who did not.

[figure not shown]
In a separate analysis based on COPD-36 sample, cost during the first year after incident COPD diagnosis will be compared with costs in the second and third year after incident diagnosis.

[figure not shown]
[figure not shown]
Table 3 HCRU and direct healthcare cost definition

Item	HCRU	Cost
COPD medication	
• Nb. of prescriptions for medications as reported in Suppl. Table 2, per agent type• Nb. of prescribed DDDs for medications as reported in Suppl. Table 2, per agent type	
• Drug cost (based on list prices) for medications as reported in Suppl. Table 2.
Other medications	
• Nb. of non COPD-medications, defined as at least 2 prescriptions of an agent (on third level of ATC groups)• Antibiotics for systemic use (ATC J02AA) and antibiotics in combination with corticosteroids (ATC D07C)	
• Drug cost of prescribed non-COPD medications
Outpatient treatment	
• Nb. of GP visits• Nb. of pneumologist visits• Nb. of other outpatient specialist visits	
• Cost of outpatient visits as defined in the HCRU column, based on the proxy of “treatment points”
Hospitalizations	
• Nb. of hospitalizations with a COPD-exacerbation (J44.1) including mean duration of stay in days• Nb. of hospitalizations with any COPD diagnosis as main diagnosis (J44.-) including mean duration of stay• Other non-COPD hospitalizations including mean duration of stay in days• Time to first all-cause hospitalization	
• Cost for hospitalizations as defined in the HCRU column

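### Severe exacerbations are counted from J44.1 alone, with no stated reason and no visible sensitivity analysis; if some J44.0 admissions are exacerbations, the severe rate is too low and guideline non-adherence at triple therapy too high

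*Combined protocol and SAP*

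**What the plan says.** Section 9.3.2.2 (Second Secondary) gives the operative definition. In the main analysis "only severe exacerbations leading to an inpatient hospitalization (COPD exacerbation documented as main diagnosis: ICD-10 J44.1) will be considered". The abstract's variable list matches it with "hospitalizations with a COPD exacerbation as main diagnosis (ICD-10 J44.1"), as a subset of "hospitalizations with COPD as main diagnosis (ICD-10 J44".-). Table 3 keeps the same two levels. It has one line for exacerbation stays (J44.1) and a separate one for "Nb. of hospitalizations with any COPD diagnosis as main diagnosis (J44.-) including mean duration of stay".

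The reason offered begins "Because of the higher diagnosis validity, in the main analysis". Nothing in the visible text says why J44.1 is the only J44 subcode that qualifies.

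Outside hospital, coded exacerbations also use J44.1: "Exacerbations as documented by outpatient pneumologists (ICD-10 J44.1"). A separate analysis of non-severe events uses prescriptions instead: "prescriptions of SCS/OCS either separately or in combination with antibiotics, will be considered as proxy for the treatment of a non-severe exacerbation".

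The First Secondary outcome uses J44.1 again. For patients who start triple therapy after the index date, COPD-12 scores a patient as not in line with the guidelines when there is at most one confirmed outpatient exacerbation diagnosis and "no inpatient diagnosis of a COPD exacerbation (ICD-10 J44.1) before date of prescription of a triple therapy". COPD DMP-12 uses the same code condition and, for the 2012 guideline only, adds DMP-documented exacerbations and FEV₁.

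**The concern.** The objective is to describe severe exacerbations that lead to hospital admission. The plan measures this with one code, while treating J44.1 admissions as a subset of all admissions with COPD as main diagnosis. Whether the rest of that set contains exacerbations is left open.

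The validity argument does not settle it. It explains why inpatient diagnoses are preferred to outpatient ones. Section 9.4 rates inpatient coding as valid because it drives reimbursement, and that applies to every inpatient J44 subcode alike.

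The code that matters most is probably J44.0. The documents never name it. On the assumption about its title, an acute COPD admission with a lower respiratory infection could carry J44.0 as main diagnosis. It would then be counted as a COPD admission and not as a severe exacerbation.

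Two sets of results depend on this:
- **Objective C:** the percentage of patients with a severe exacerbation, the rate per patient-year, and the time to first exacerbation (Table 4).
- **Objective B:** the percentage not in line with the guidelines at first triple therapy. A patient whose only qualifying admission was coded J44.0, with at most one outpatient J44.1, would be scored as not in line.

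The restriction can only lower the severe count, and it can only raise the not-in-line percentage.

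**Working it through.** The plan states no exacerbation rate, power or sample size that depends on the code list, so there is no figure to reproduce. What follows is a range under stated assumptions.

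**Inputs**
- Counted as severe: J44.1 main-diagnosis stays (section 9.3.2.2, abstract).
- s: J44.0 stays as a share of J44.0 plus J44.1 main-diagnosis stays. Not in the documents; assumed 10%, 30% and 50%.
- g: share of J44.0 stays that are true exacerbations. Not in the documents; assumed 0, 0.5 and 1.
- All J44.1 main-diagnosis stays are taken as true exacerbations. Other J44 subcodes are left out of the calculation.

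**Formulas, per J44.0 or J44.1 stay**
- Counted events: 1 − s
- True events: 1 − s + s·g
- Relative understatement: s·g / (1 − s + s·g)
- True rate over counted rate: (1 − s + s·g) / (1 − s)

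**Example.** Take 100 stays with s = 30% and g = 0.5. There are 70 J44.1 stays, all counted, and 30 J44.0 stays, of which 15 are true exacerbations. True events are 70 + 15 = 85. The understatement is 15/85 = 17.6%, and the ratio is 85/70 = 1.21.

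| s | g | Understatement | True / counted |
|---|---|---|---|
| 10% | 0 | 0% | 1.00 |
| 10% | 0.5 | 5.3% | 1.06 |
| 10% | 1 | 10% | 1.11 |
| 30% | 0 | 0% | 1.00 |
| 30% | 0.5 | 17.6% | 1.21 |
| 30% | 1 | 30% | 1.43 |
| 50% | 0 | 0% | 1.00 |
| 50% | 0.5 | 33.3% | 1.50 |
| 50% | 1 | 50% | 2.00 |

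These figures apply to the event rate. The percentage with at least one event and the time to first event also depend on how J44.0 and J44.1 stays fall within the same patients, which the documents do not show.

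**Triple-therapy rule.** No arithmetic is possible. To be scored not in line because of the code choice, a patient must meet three conditions before the first triple prescription: at most one confirmed outpatient J44.1, no inpatient J44.1, and an admission under J44.0 that was a severe exacerbation. The inpatient condition is not limited to the main diagnosis, so a J44.1 in any inpatient position prevents the score. The group may be small, but it cannot be sized from the documents.

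**The case against.** The case for leaving the plan alone has several parts.

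- **The meaning of J44.0 is not in the documents.** This stands. The title is an assumption to be checked. The part that needs no outside source is that J44.1 is one subset of the J44.- admissions, chosen without a reason and without a visible test.
- **J44.1 is the code the plan labels as exacerbation, so it favours specificity.** This stands as a reason to keep it as the main definition. Some J44.0 stays may be infections without an exacerbation.
- **The excluded stays are not lost.** Correct: they are in the J44.- count. That count is resource use, however, and is not broken down by subcode, so a reader could not recover the effect.
- **The DMP analysis may capture them.** Table 4 adds DMP documentation to the inpatient codes, and Supplemental Table 1 lists a variable for emergency inpatient treatment due to COPD with no subcode limit. The plan does not say which DMP variable it will use, and this reaches only the DMP samples.
- **Parts of the outcome and analysis sections are blacked out.** For that reason the absence of a sensitivity analysis is claimed for the visible text only.

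A reader might also infer that the plan contradicts itself by counting infective episodes as exacerbations outside hospital but not inside. The documents do not support this. The outpatient proxy requires a systemic or oral corticosteroid, antibiotics are an optional addition, and no infection diagnosis is used. An infection treated with antibiotics alone is not counted, and coded outpatient exacerbations are J44.1 only.

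**Conclusion.** The point holds in conditional form. The code restriction is unexplained and, in the visible text, untested. Its possible effect runs one way: a severe rate that is too low, and a not-in-line percentage at triple therapy that is too high.

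The size is unknown. Over the assumed range it is 0% to 50% of the true rate, and it is zero if no J44.0 stay is an exacerbation. It rests on the J44.0 title being as assumed and on some J44.0 stays being exacerbations.

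Two stronger conclusions do not follow. One is that the severe rate is understated by the whole J44.0 share; that is the g = 1 row only. The other is that J44.0 plus J44.1 must become the primary definition. That trades specificity for sensitivity, and the documents contain nothing to decide it.

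**What to change.** 1. **Section 9.3.2.2 (Second Secondary) and Table 4.** Keep J44.1 as main diagnosis for the main analysis and state why. Add a pre-specified sensitivity analysis that defines a severe exacerbation as a stay with J44.0 or J44.1 as main diagnosis. Report the percentage of patients, the rate per patient-year and the time to first event. Check the J44.0 title in the ICD-10-GM versions that cover the study years.
2. **Table 3.** Break the planned J44.- main-diagnosis count down by subcode. Its total is the upper bound for any severe-exacerbation definition based on COPD as main diagnosis.
3. **First Secondary, triple-therapy rule (COPD-12 and COPD DMP-12).** Repeat the inpatient part with J44.0 added, and say whether J44.0 must be the main diagnosis or may stand in any inpatient position, since the present rule does not restrict this.

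The cost is wording, one more code in the query and a few more table rows. The main-diagnosis J44.0 stays are already inside the planned J44.- count, so steps 1 and 2 need no further extraction. The drawback is that some J44.0 stays may be infections without an exacerbation, so the sensitivity result should be read as the upper end for these two codes and not as a corrected rate.

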5. AMENDMENTS AND UPDATES

None

6. MILESTONES

Milestone	Planned Date
Draft of study protocol	
First Steering Board Meeting	
Final study protocol & approval by [REDACTED]	
Start of data collection (Start of data access/ data validation)	
End of data collection (End of data analysis)	
Final report of study results (Final Steering Board Meeting)	
Finalization of publication drafts	

[figure not shown]
7. RATIONALE AND BACKGROUND

In terms of chronic obstructive pulmonary disease (COPD) drug therapy, the current German COPD guideline (S2) [1] recommends a treatment escalation procedure (Figure 1). For incident COPD patients (for the sake of simplicity, newly diagnosed and so far treatment naïve COPD patients will be referred to as “incident COPD patients” in the following), the guideline recommends the following:

- No treatment (low symptom burden) or
- Short-acting beta antagonist (SABA) or short-acting muscarinic antagonist (SAMA) or
- Long-acting beta agonist (LABA) or long-acting muscarinic antagonist (LAMA) or LABA+LAMA.

All other treatments, particularly combination treatments including inhaled corticosteroids (ICS), are only recommended as escalation therapy. However, despite the increasing evidence (e.g. WISDOM study [3], FLAME study [4]), there might exist the view that early use of ICS in the treatment of COPD might be advisable, and might be prescribed in a substantial percentage of COPD-incident patients.

Figure 1 Treatment recommendations with regard to COPD stages, according to German 2018 S2 guideline [1]

Medikamentöse Dauertherapie der COPD	
Symptome - Ausmaß der Lungenfunktions-einschränkungen berücksichtigen	Medikamentöse Therapie
Wenig (z. B. CAT < 10) GOLD Gruppe A	- Keine - SABA + SAMA (initial) - LABA oder LAMA
Viel (z. B. CAT \geq 10) GOLD Gruppe B	- LABA oder LAMA - LABA + LAMA
Exazerbationen > 1 oder Exazerbation mit Hospitalisierung GOLD Gruppen C und D	
Nicht vorbehandelt	LAMA oder LAMA + LABA
Vorbehandelt	LAMA + LABA
Eskalation/Wechsel	 LABA + ICS → LAMA + LABA + ICS
	\pm Roflumilast (Phänotyp chronische Bronchitis)

Currently, knowledge on real world treatment of incident COPD patients in Germany is sparse, in particular regarding the frequency of different drug therapy prescriptions and the frequency of early therapy escalation including ICS. With the current analyses, we aim to emphasize the central role of LAMA/LABA therapy in COPD and importance of treatment guideline adherence.

This study aims to address the question of guideline adherence by reporting treatment of incident COPD patients as well as description of COPD-associated outcomes, especially severe exacerbations leading to hospitalization. In addition, real-world treatment of incident COPD patients will be compared to German guidelines, using current 2018 guidelines and 2012 guidelines as framework in two scenario calculations. The results of this study could serve as basis for the tailored development of managed care projects together with payers.

8. RESEARCH QUESTION AND OBJECTIVES

[figure not shown]
The main research questions of this study can be summarized as follows:

PRIMARY

- Description of the real-life drug treatment of patients with incident COPD, including description of treatment sequence/escalation in the first 12/24/36 months after incident diagnosis

SECONDARY

- Comparison of initial drug treatment of incident COPD patients with two versions of German treatment guidelines (2012/2018)
- Description of exacerbation frequency (severe exacerbations associated with an inpatient hospitalization) of incident COPD patients in the first 12/24/36 months after incident diagnosis
- Description of health-care resource use (HCRU; including use of long-term oxygen therapy (LTOT)) and direct treatment cost of incident COPD patients in the first 12/24/36 months after incident diagnosis

9. RESEARCH METHODS

9.1 STUDY DESIGN

A retrospective analysis will be done based on a claims dataset delivered by two German sickness funds (so far, a cooperation with [REDACTED] is planned, second sickness fund needs to be named yet). The dataset will cover the period 01/01/2013-30/06/2018⁷. In selected analyses, incident COPD patients will be observed for an exact follow-up period of 12 months (in subgroup analyses: 24 and 36 months); censoring of patients will only be done in case a patient died during the respective follow-up period. [REDACTED]

The data will be analyzed for a pre-index period (12 months before index diagnosis) and for a follow-up period of 12 months after index date. In subgroup analyses, longer follow-ups (24 and 36 months, and full observation time (up to 54 months⁸)), are used. Death after index diagnosis during the follow-up is the only accepted exception from this rule. For a subsample of patients, disease management program (DMP) data might be available. These provide disease specifics such as forced expiratory volume in 1 second (FEV₁) values, specifics of prescribed therapy, and exacerbation frequency and severity.

The dataset contains available information on the sociodemographic characteristics of the patients, their treatment with prescription aids and medications, their outpatient and inpatient treatment, and COPD-specific clinical parameters for the patients who participated in a disease management program (DMP). A first overview of data generally available in claims data of a German sickness fund is given in Table 1. The study-specific data set (required data according to approved study protocol) needs to be approved by the respective sickness funds, based on the study objectives and the respective methodology as outlined in this protocol.

⁷ If more data will be available until time of analysis start, further quarters (from 2018) will be included into the analysis.

⁸ If more data will be available until time of analysis start, further quarters (from 2018) will be included into the analysis.

[figure not shown]
Table 1 Data generally available in the claims data set

Sociodemographic characteristics	Inpatient care	Outpatient care	Outpatient medication (prescriptions only)	Other data
• Age	• Data about initial diagnoses including day of admission	• All physicians' visits including type of physician (esp. GPs and specialists in different specialist groups)	• Type of medication (medication number – in Germany: PZN), ATC code, number of packs, dates of prescription and of dispensing pharmacy	• Costs for outpatient devices/other supportive measures • Outpatient surgeries
• Gender	• All documented diagnoses/ procedures	• Documentation of diagnoses/ measures (EBM, GONr, OPS)	• Prescribing physician	• Other services paid by the insurance, e.g. salary co-payments etc. and Costs of other diagnostic/ therapeutic measures
• Type of insurance	• Length of stay in days	• Description of "safety" of diagnoses	• Medication-specific data (DDD, other information)	• Outpatient/in-patient long-term care data
• Partly: Socioeconomic status	• Costs including specific DRG	• Dates (physician visits; all diagnostic/ therapeutic measures)	• Costs; indirectly by calculation: patients' co-payments	• Days absent from work
• Mortality	• Data about inpatient/ outpatient rehabilitation clinic stays/other follow-up measures	• Costs of outpatient care based on activity points documented by doctors		• Partly DMP data: FEV ₁ , need for COPD medication, exacerbations (Suppl. Table 1)

For the claims data analysis, [REDACTED] will involve its university-affiliated partner, [REDACTED] has a longstanding experience in claims data analyses. [REDACTED] will close a contract with the cooperating sickness funds. This includes a detailed and mutually agreed list defining data extraction inclusion/exclusion criteria as well as all variables and formats to be used. Moreover, the contract outlines which data protection measures need to be implemented by [REDACTED]. The sickness funds will participate in the Steering Board of the study as well as being a co-author of all future publications of study results. The general model of cooperation is shown in Figure 2.

Figure 2

General study organization

In a first meeting of the Steering board, the study protocol draft will be discussed and, finally, be approved. After the approval of the steering board, the protocol will be submitted to the cooperating sickness funds and BI for final approval.

